## **11 STUDY SUBJECTS**

### **11.1 Subject Enrollment and Disposition**

#### **11.1.1 Screened and Enrolled Subjects**

Screening, enrollment and disposition will be summarized by country and by investigator for each treatment group and overall.

The percentages will be based on total subjects who enrolled in Run-in Period of the study. A subject listing will be provided with the above information, as well as geographic region, country, and site ID for subjects who were screened and enrolled in the Run-in Period, but not randomized.

#### **11.1.2 Randomized Subjects**

Dispositions of randomized subjects will be summarized by treatment group (including dose level) and overall. An additional summary will be included for subjects who were randomized and dose escalated. The subject disposition summary will include Parts A, B, and C of the Treatment Period.

A listing of disposition will be provided for all randomized subjects. A separated listing will present subjects who are excluded from SAF, RSAF, ITT, mITT or PP analysis sets, along with reasons for the exclusions.

### **11.2 Protocol Deviations**

Protocol deviations will be listed by deviation type (e.g., major) and category (e.g., noncompliance with study procedures or restrictions). All deviations will be identified prior to database lock and will be summarized and presented in listing(s); listings will include flags for deviation type (major or minor). Major protocol deviations are defined per *Guideline for Industry: Structure and Content of Clinical Study* from International Council for Harmonisation

(ICH E3) guidance. All protocol deviations and major protocol deviations will be summarized by deviation category and type. In addition, a listing of all deviations and major protocol deviations will be provided.

### **11.3 Demographics and Baseline Characteristics**

Demographics and baseline characteristics will be summarized and listed for all randomized subjects (ITT).

#### **11.3.1 Demographics**

Demographic characteristics will include age, age category ( $\leq$  30 years,  $\rightarrow$  30 years;  $\leq$  median age of ITT Analysis Set,  $>$  median age of ITT Analysis Set), sex, race, ethnicity, and geographic region. A subject listing of demographics will be provided.

#### **11.3.2 Baseline Characteristics**

The following baseline characteristics will be summarized. They will be listed in subject listings in the following categories:

- Serum hormones (baseline value [Section 9.3.10])
- Metabolic baseline characteristics
  - Weight profile
    - Weight
    - Body mass index
    - Body mass index classification
    - Body surface area
  - Insulin Profile
    - HbA1c
    - Fasting glucose
    - Fasting insulin
    - HOMA-IR
  - Lipid Profile
    - Total cholesterol
    - LDL cholesterol
  - Blood Pressure Profile
    - Systolic blood pressure
    - diastolic blood pressure
- Quality of life assessments (SF-36 total score)

- Acne assessments
- Hirsutism assessments
- Lesion volume of TART(s)

## **11.4 Medical History**

Medical history and CAH history will be summarized by randomized treatment group and dose level for ITT subjects. Individual subject listings will include subject identification number and randomized treatment/dose level (if a subject is randomized), along with general history and CAH history data collected from eCRF, for all enrolled subjects (i.e., who participated in the Run-in Period).

### **11.4.1 General Medical History**

General medical history, besides CAH, will be mapped to preferred terms and system organ classes using the Medical Dictionary for Regulatory Activities (MedDRA®) Dictionary (version 23.0). General medical history will be summarized by system organ class (SOC) and preferred term (PT). A subject listing of general medical history will include start date/end date, verbatim medical history term, SOC, PT, and ongoing status.

### **11.4.2 Congenital Adrenal Hyperplasia History**

#### **11.4.2.1 Signs and Symptoms**

Age at CAH diagnosis, type of CAH, and the signs and/or symptoms of CAH will be summarized. The most bothersome signs and/or symptoms of CAH will also be summarized. Signs and/or symptoms of CAH will be included in a subject listing.

#### **11.4.2.2 Glucocorticoid History**

The Baseline (Week 6) GC dose level in HCe, GC therapy medication(s), reasons for change to the current background GC therapy (if changed therapy) will be summarized. A subject listing will include all summarized variables, as well as any higher/lower dose of GC during adulthood, reason to reduce/increase to the current GC dose.

#### **11.4.2.3 Hospital and Stress Dosing History**

Hospitalization and stress dosing history will be summarized separately and will include the frequency and percentage of subjects with at least: a) one hospitalization for adrenal insufficiency/crisis in the past 5 years, b) at least one hospitalization for adrenal insufficiency/crisis in the past 12 months, c) at least one stress dosing event in the past 12 months. A subject listing will be included.

### **12 STUDY DRUG AND OTHER MEDICATIONS**

#### **12.1 Exposure to Study Drug and Study Treatment Compliance**

Summaries of study drug exposure and compliance will be summarized overall and separately for those taken during Part A, Part B, and Part C of the study. The source for study drug dosing and compliance is drug accountability.

The summaries will include the total number of doses taken, mean daily dose (mg/day), duration (days) of exposure, and study drug compliance (see definitions in [Section 9.3.23.4](#)) by treatment group and dose level. A subject who received multiple dose levels of tildacerfont will be included in each of the dose levels for the purpose of summarization in separate rows for subjects with a dose escalation.

Furthermore, number and percentage of subjects with and without dose escalation of study drug will be summarized by randomized treatment group and dose level received for the overall summary. The denominators for percentages will be the number of subjects who received the randomized study drug treatment.

The drug accountability information, including number of tablets dispensed, number of tablets returned, number of tablets lost or destroyed, along with all summarized variables, will be listed in subject listings. Study drug diary compliance will be listed from the Run-in Period through the end of Part A, and all diary entry records will be provided in a separate listing.

## **12.2 Glucocorticoid Therapy**

Concomitant GC therapy will be summarized overall and separately for those taken during Part A, Part B and Part C of the study. The source of GC dosing is the Prior & Concomitant Daily Glucocorticoids/Mineralocorticoids eCRF.

The following items will be summarized, overall GC diary compliance ([Section 9.3.23.7](#)), GC compliance by GC therapy type (i.e., hydrocortisone, prednisolone, prednisone, methylprednisolone, or other), proportion of subjects with a stress dosing event, number of unique stress dosing events ([Section 9.3.26.4](#)), duration of stress dosing events. All the above information will be included in a subject listing.

## **12.3 Prior and Concomitant Medications**

All medication verbatim terms reported on the electronic case report form (eCRFs) will be mapped according to the World Health Organization (WHO) Drug Dictionary (WHO DD March 2020 B3). The medications will be mapped to Anatomical/Therapeutic/Chemical (ATC) class and preferred names.

Prior and concomitant medications (see definition in [Section 9.3.24](#)), other than glucocorticoids, will be summarized using WHO DD ATC class and preferred name. The summary results will be presented by treatment/dose level and Treatment Period (Part A, Part B, and Part C). Prior medications will be summarized by randomized treatment group. Concomitant medications will be summarized by actual dose taken concomitantly during each treatment period. For Part A, medications will be summarized by the actual randomized dose. For Part B, medications will be summarized under the treatment at the start of the medication. A subject who does-escalates in Part B will be counted within the denominator of each treatment group that s/he received. For example, a subject who started at 50 mg of tildacerfont, escalated to 100 mg of tildacerfont, and escalated again to 200 mg tildacerfont will be counted in all three dose levels; the medication that the subject starts during the treatment period will be counted once under the dose level that

the subject was taking at the start of the medication. For Part C, all subjects will receive 200 mg tildacerfont.

These summaries will present the number and percentage of subjects using each medication. Subjects may have more than one medication within an ATC class and preferred name. At each summary level subjects are counted once if they reported one or more medications at that level. Each summary will be ordered by descending frequency of incidence of ATC class and preferred name within each ATC class.

All medications will be provided in a subject listing with flags indicating study drug dose level. The variables include, but not limited to: Start date/end date/ongoing, medication name, ATC class and preferred name, indication, dose, unit, form, frequency, and route.

## **13 EFFICACY ANALYSES**

### **13.1 Primary Efficacy Analysis**

The Primary Efficacy Analysis is planned after all subjects have completed the study Week 18 visit in Part A of the study. During this first 12-week double-blind, placebo-controlled treatment period, there will be no dose escalation. The scheduled visits included in this treatment period include study Week 10, Week 14, and Week 18 corresponding respectively to 4, 8 and 12 weeks of double-blind randomized treatment. Efficacy Analyses will focus on inferences between tildacerfont treated subjects and placebo treated subjects. As shown in [Table 1](#), the Primary Efficacy Analysis (1.1), the five Secondary Efficacy Analyses (2.1, 2.2, 2.3, 2.4 and 2.5), and selected Exploratory Efficacy Analyses (3.1 to 3.6 and 3.15) will be analyzed at the primary analysis. These Efficacy Analyses will be performed using the ITT Analysis Set ([Section 8.2](#)) as the main analyses.

### **13.2 Final Efficacy Analysis**

The Final Efficacy Analysis will occur after the last subject has completed the study Week 76 visit or if the study is discontinued by the Sponsor. The data from study Week 18 through Week 76 will be frozen prior to the final analysis.

The scheduled visits included in this treatment period include study Week 24, Week 30, Week 38, Week 46, Week 58, Week 70, Week 76 visits. Exploratory Efficacy Analyses 3.7 to 3.11 and Safety Endpoints 5.1, as shown in [Table 1](#), will be analyzed at the final analysis.

### **13.3 Primary Efficacy Analysis**

The primary objective of the study is to evaluate the effect of tildacerfont in controlling A4 levels in adult subjects with classic CAH who have elevated biomarkers at baseline on their current, dose of GC replacement therapy over the 12-week, double-blind, placebo-controlled Part A of the Treatment Period. This objective will be achieved via A4 dose response analysis.

#### **13.3.1 Definition of A4 Dose Response Analysis**

The A4 dose response analysis is defined as follows:

**Population:** The analysis will be executed on a “treatment policy” basis, i.e. in the ITT analysis set, including all classic CAH subjects who were randomized into the study.

**Variable:** The analysis variable is the log-transformed change from baseline in serum A4 over the 12 week double blind period. The log-transformed change is calculated as  $\log(\text{A4 post baseline value}) - \log(\text{A4 baseline value})$

**Intercurrent events:** For the Primary Efficacy Analysis (and all Secondary Efficacy Analyses), intercurrent events such as changes in GC type or lack of treatment compliance or GC compliance, treatment interruption or discontinuation, use of prohibited medications are irrelevant as primary endpoint data are collected regardless and are included in the primary analysis. Stress dosing is also an intercurrent event that can substantially suppress A4 values and confound treatment effect. To adjust for this intercurrent event, the protocol design (Protocol

Section 6.5.1.5) has measures to minimize the impact of stress dosing on the primary endpoint, such as the delay of scheduled lab draws until 5 days after the subject has returned to their prescribed GC regimen.

### 13.3.2 Dose Response Statistical Hypothesis

For the Primary Efficacy Analysis, the null hypothesis is that there is no difference in the profile of log A4 change from baseline through 12 weeks of blinded randomized treatment between tildacerfont and placebo. The alternative hypothesis is that there is difference in the profile of log A4 change from baseline through 12 weeks of blinded randomized treatment between tildacerfont and placebo.

To assess this dose response hypothesis, repeated measures random coefficients mixed-effects model will be used:

$$y_{ijt} = (\beta_0 + \xi_i) + (\beta_1 + \eta_i)t + (\beta_2 + \theta_i)t^2 + \beta_{4j}I_j + \beta_{5j}I_jt + \beta_{6j}I_jt^2 + \beta_7\kappa + \beta_8G + \beta_9D + e_{ijt}$$

where:

$y_{ijt}$  is the log A4 change from baseline value for subject  $i$ ,  $i = 1, \dots, N$ , at time  $t$  in treatment group  $j$ ,  $j = 1, 2, 3, 4$  (1 = 200mg tildacerfont, 2 = 100mg tildacerfont, 3 = 50mg tildacerfont and 4 = placebo),  $I_t$  is the indicator for randomised treatment ( $I_t = 1$  for tildacerfont 200mg,  $=2$  for 100mg,  $=3$  for 50mg and  $=4$  for placebo),  $\kappa$  is log baseline A4 value,  $G$  is the indicator for sex ( $G = 1$  male,  $G = 0$  female) and  $D$  baseline GC dose (in HCe),

$\beta_0$  is the fixed intercept effect.

$\beta_1$  is the fixed effect of the linear component of time

$\beta_2$  is the fixed effect of the quadratic component of time

$\beta_{4j}$  is the fixed effect of treatment  $j$  parametrized such with  $\beta_{44} = 0$

$\beta_{5j}$  is the effect of treatment  $j$  on the linear component of time parametrized such that  $\beta_{54} = 0$

$\beta_{6j}$  is the effect of treatment  $j$  on the quadratic component of time parametrized such that  $\beta_{64} = 0$

$\beta_7$  is the fixed effect of baseline log A4

$\beta_8$  is the fixed effect of gender

$\beta_9$  is the fixed effect of baseline GC dose

$\xi_i$  is the random effect of subject  $i$  on the intercept

$\eta_i$  is the random effect of subject  $i$  on the linear component of time

$\theta_i$  is the random effect of subject  $i$  on the quadratic component of time

$e_{ijt}$  is the random error for subject  $i$  on treatment  $j$  and time  $t$ .

The random effects,  $\xi_i$ ,  $\eta_i$ , and  $\theta_i$  are assumed independent and identically normally distributed with variance components  $\sigma_\xi^2$ ,  $\sigma_\eta^2$ , and  $\sigma_\theta^2$ , and, independently, the random error  $e_{ij}$  is normally distributed with variance  $\sigma^2$ .

The dose response Primary Efficacy Analysis therefore corresponds to the formal hypothesis statement,

$H_{0L}: \beta_{51} = \beta_{52} = \beta_{53} = 0$  vs  $H_{1L}: \beta_{5j} \neq 0$  for at least one  $j$

and

$H_{0Q}: \beta_{61} = \beta_{62} = \beta_{63} = 0$  vs  $H_{1Q}: \beta_{6j} \neq 0$  for at least one  $j$

The union intersection hypothesis  $H_{0L} \cap H_{0Q}$  represents the null that there is no dose response for tildacerfont versus placebo.

### 13.3.3 Dose Response Modeling and Testing

Statistical testing for dose response will be performed using the repeated measures random coefficients mixed-effects model described in [Section 13.3.2](#). A4 values will be log transformed prior to analysis. The model will comprise of the log A4 change from baseline through to study Week 18, i.e. though 12 weeks of double blind randomized treatment; note the actual time, in days, from baseline to each post baseline A4 value through to study week 18 will be used in this analysis. Randomized treatment group and sex will be included in the model as class factors and baseline GC dose (in HCe) as continuous covariate. Subject specific intercept, time (in days)

and time x time random effects will be included. Further, randomized treatment by time and randomized treatment by time x time interactions will be included. The model will be fitted using maximum likelihood estimation. If the variance component for time or time x time are estimated to be zero then the corresponding term (or terms) will be retained in the model as fixed effects and the analysis re-run.

To test the union intersection hypothesis  $H_{0L} \cap H_{QL}$ , the model will be fitted with and without the randomized treatment by time and randomized treatment by time squared interactions terms. The difference in -2 log likelihood between models will be compared to the  $\chi^2_{df}$  cumulative distribution function on the appropriate degrees of freedom (i.e.  $df = 6$ ), this will provide the p-value to determine if the union intersection hypothesis can be rejected at the 10% alpha level; if so then there is evidence for a treatment effect of tildercerfont over placebo.

The fitted A4 change from baseline versus time profile will be extracted from the model for each randomized treatment and displayed graphically, superimposed upon the A4 time profiles for individual subjects.

Note, the programming of the repeated measures random coefficients mixed-effects model is particularly complex, hence example SAS codes perform the analysis are presented in Appendix D.

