### 13.3.5.1 Imputation of A4 values for Missing Data

Missing data can have an adverse effect on the estimation of endpoints. As such, multiple imputation of missing data via retrieved drop-out method will be used for the primary analysis. Retrieved drop-outs are defined as subjects who prematurely discontinue study drug treatment but remain in the study and still have assessments collected at the remaining scheduled visits in the study. These subjects can provide data that is reflective of subjects who discontinue treatment early without collection of assessments. Prior to performing the MI with retrieved drop-out, all intermittent (non-monotone) missing data will be imputed assuming missing at random (MAR).

A total of 20 datasets will be stochastically imputed for each intermittent missing A4 value at Week 18 using a mixed model repeated measures (MMRM) model. In this model A4 values will be log transformed prior to analysis. The model will comprise of the log A4 values at visits 5, 6 and 7 (= study weeks 10, 14 and 18) as the dependent variable with subject as random effect; randomized treatment group (0 = placebo, 50 = 50 mg QD tildacerfont, 100 = 100 mg QD tildacerfont, and 200 = 200 mg QD tildacerfont), time (=visit), sex (0=male, 1=female), and the interaction of treatment and time as fixed effects; and the log-transformed baseline serum A4 and the baseline GC dose (in HCe) as continuous covariates in the model. Within-subject correlations will be modeled using an unstructured covariance structure. Time ordering is a repeated measure within subjects. Errors for different subjects are assumed to be independent with an unstructured covariance structure.

In the event the MMRM model with an unstructured covariance structure does not converge, the following covariance structures will be used as substitution in the order below. Each subsequent covariance structure will be used only if each previous covariance structure was used and the model did not converge.

- a) Toeplitz covariance structure (assuming measurements from samples taken closer together in time are more highly correlated than those from samples taken farther apart)

- b) First order of auto-regressive [AR(1)] covariance structure (assuming measurements from samples taken closer together in time are more highly correlated than those from samples taken farther apart)

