### 13.4.1 First Secondary Efficacy Analysis

The First Secondary Efficacy Analysis (see [Table 1](#), Analysis 2.1) relates to the change from baseline in A4 as assessed on the log scale after 12 weeks on double-blind, placebo-controlled treatment. This analysis will be achieved as an integral part of the dose response modelling as described in [Section 13.3.3](#).

The estimated mean change from baseline in log A4 values at 4, 8 and 12 weeks of double blind randomized treatment will be extracted from the model by treatment arm as will the difference and associated 95% CI and p-value between each tildacerfont dose and placebo at each of 4, 8 and 12 weeks. To facilitate ease of interpretation, the estimated mean change from baseline in log A4 for each tildacerfont dose and placebo will be back transformed resulting in the estimated ratio of geometric means to baseline, i.e. the back transformed log scale estimated mean change becomes  $\{\text{estimated A4 geometric mean at time } x\}/\{\text{estimated A4 geometric mean at baseline}\}$  = GMR. Hence, GMR – 1 becomes the percentage CFB in geometric means. Further, the difference between each tildacerfont dose and placebo in estimated mean change from baseline in log A4 (along with the associated 95% CI) will also back transformed resulting in the ratio of  $\{\text{A4 GMR tilda at time } x\}/\{\text{A4 GMR placebo at time } x\}$  as the measure of treatment effect. And, again,  $\{\text{A4 GMR tilda at time } x\}/\{\text{A4 GMR placebo at time } x\} - 1$  becomes the percentage reduction (or increase) in geometric mean A4 values at time  $x$  for tildacerfont compared to placebo.

In addition orthogonal linear and quadratic contrasts between treatments at 12 weeks of double blind randomized treatment will also be estimated as a supportive measure of dose response at this time point.

Example SAS codes in relation to the First Secondary Efficacy Analysis are provided in Appendix D.

A serial plot will be presented of the estimated mean change from baseline in log A4 over time. The y-axis will be the percent CFB (i.e  $100 \{ \exp(\text{estimated change from baseline in log A4}) - 1 \}$ ) and the x-axis will represent the Part A visits, baseline, Week 4, Week 8, and Week 12 of double blind randomized treatment. All treatment groups will be presented on the graph.

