### **13.5.5 Correlation of A4 Level versus 17-OHP Level**

The Exploratory Efficacy Analysis 3.5 in [Table 1](#) is the within subject correlation of A4 Level versus 17-OHP Level. This will be assessed on the log scale by randomized treatment arm. Within a given treatment arm, the data will be organized within subject as follows: (i) dummy variable ‘vtype’= 1 for log A4 and =2 for log 17-OHP; (ii) dummy variable ‘replicate’ = 1 for

baseline, =2 for study Week 10, =3 for study Week 14 and =4 for study Week 18; and (iii) variable ‘val’ = value of log A4 or log 17-OHP. SAS code will be for the form,

```
PROC MIXED METHOD=ML DATA=X;
CLASS SUBJECT VTYPE REPLICATE;
MODEL VAL = VTYPE / SOLUTION DDFM=KR;
RANDOM VTYPE /TYPE=UN SUBJECT= SUBJECT V VCORR;
REPEATED VTYPE / TYPE=UN SUBJECT=REPLICATE (SUBJECT) ;
RUN;
```

The estimated correlation coefficient will be extracted from the VCORR matrix estimate and presented by randomized treatment arm.

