LBASE=LOG (BASE) ;
LCFB=LPULSE-LBASE;
RUN;
DATA STUDY2;
  SET STUDY2;
  G=EXERTYPE;
RUN;

PROC SORT DATA=STUDY2;
  BY ID TIME;
RUN;

** FULL MODEL WITH TIME*G AND TIME*TIME*G = DOSE RESPONSE PARAMETERS **;

PROC MIXED DATA=STUDY2 COVTEST NOCLPRINT METHOD=ML ;
  CLASS ID G ;
  MODEL PULSE = BASE TIME G TIME*G TIME*TIME TIME*TIME*G /
  SOLUTION OUTP=PRED1RX OUTPM = PRED1FX;
  RANDOM INTERCEPT TIME TIME*TIME / SUBJECT = ID SOLUTION;

  ** ESTIMATES WHEN BASELINE = 90 BPM, I.E. LOG BASE = 4.5 **;
ESTIMATE "INTERCEPT: 1 " INTERCEPT 1 BASE 90 G 1 0 0 ;
ESTIMATE "INTERCEPT: 2 " INTERCEPT 1 BASE 90 G 0 1 0 ;
ESTIMATE "INTERCEPT: 3 " INTERCEPT 1 BASE 90 G 0 0 1 ;

  ** TRT EFFECTS AND CONTRASTSAT 600 DAYS **;

ESTIMATE "VALUE AT 600 1" INTERCEPT 1 BASE 90 G 1 0 0 TIME 600 G*TIME 600 0 0
TIME*TIME 360000 G*TIME*TIME 360000 0 0 ;
ESTIMATE "VALUE AT 600 2" INTERCEPT 1 BASE 90 G 0 1 0 TIME 600 G*TIME 0 600 0
TIME*TIME 360000 G*TIME*TIME 0 360000 0 ;
ESTIMATE "VALUE AT 600 3" INTERCEPT 1 BASE 90 G 0 0 1 TIME 600 G*TIME 0 0 600
TIME*TIME 360000 G*TIME*TIME 0 0 0 ;
ESTIMATE "VALUE AT 600 1-3" G 1 0 -1 TIME 0 G*TIME 600 0 -600 TIME*TIME 0 G*TIME*TIME 360000 0 0;
ESTIMATE "VALUE AT 600 2-3" G 0 1 -1 TIME 0 G*TIME 0 600 -600 TIME*TIME 0 G*TIME*TIME 0 360000 0 ;
ESTIMATE "LINEAR CONTRAST @ 600" G -1 0 1 TIME 0 G*TIME -600 0 600
TIME*TIME 0 G*TIME*TIME -360000 0 0;
ESTIMATE "QUADRATIC CONTRAST @ 600" G 1 -2 1 TIME 0 G*TIME 600 -1200 600
TIME*TIME 0 G*TIME*TIME 360000 -720000 0;
ODS OUTPUT FITSTATISTICS=FIT1;
ODS OUTPUT SOLUTIONF=F1;
ODS OUTPUT COVPARMS =C1;

TITLE 'RC MODEL TIME G TIME*G TIME*TIME TIME*TIME*G';
RUN;
TITLE;

** REDUCED MODEL WITH TIME*G AND TIME*TIME*G = DOSE RESPONSE PARAMETERS **;
PROC MIXED DATA=STUDY2 COVTEST NOCLPRINT METHOD=ML ;
  CLASS ID G ;
  MODEL PULSE = BASE TIME G TIME*TIME /
  SOLUTION;
  RANDOM INTERCEPT TIME TIME*TIME / SUBJECT = ID SOLUTION;

  ** ESTIMATES WHEN BASELINE = 90 BPM, I.E. LOG BASE = 4.5 **;
ESTIMATE "INTERCEPT: 1 " INTERCEPT 1 BASE 90 G 1 0 0 ;
ESTIMATE "INTERCEPT: 2 " INTERCEPT 1 BASE 90 G 0 1 0 ;
ESTIMATE "INTERCEPT: 3 " INTERCEPT 1 BASE 90 G 0 0 1 ;

  ** TRT EFFECTS AND CONTRASTSAT 600 DAYS **;
```

```
ESTIMATE "VALUE AT 600 1" INTERCEPT 1 BASE 90   G   1 0 0   TIME  600 TIME*TIME  360000  ;
ESTIMATE "VALUE AT 600 2" INTERCEPT 1 BASE 90   G   0 1 0   TIME  600 TIME*TIME  360000  ;
ESTIMATE "VALUE AT 600 3" INTERCEPT 1 BASE 90   G   0 0 1   TIME  600 TIME*TIME  360000  ;

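### The primary A4 likelihood-ratio test has no small-sample correction, so its nominal 10% level is about 11.5–13%, and no denominator-df method is named for the dose-versus-placebo contrasts

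*SAP*

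**What the plan says.** **Joint test.** SAP 13.3.3 fits the log A4 change from baseline with treatment, time, time squared and their interactions: "The model will be fitted using maximum likelihood estimation". The model is run with and without the treatment-by-time and treatment-by-time-squared terms. "The difference in -2 log likelihood between models will be compared to the" chi-square distribution on 6 df, at a 10% alpha. The example code in Appendix D agrees: "PROC MIXED DATA=STUDY2 COVTEST NOCLPRINT METHOD=ML". Neither place mentions a small-sample adjustment.

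**Random effects.** Each subject has a random intercept, slope and quadratic, coded as "RANDOM INTERCEPT TIME TIME*TIME / SUBJECT = ID SOLUTION". SAP 13.3.2 adds that these effects "are assumed independent and identically normally distributed with variance components", so there are three variances plus a residual variance. SAP 13.1 lists three post-baseline visits in Part A (Weeks 10, 14 and 18), and Appendix D removes the baseline row. Under 13.3.3, a random time or time-squared term whose variance is estimated as zero is kept only as a fixed effect and the model is re-run.

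**Contrasts.** SAP 13.4.1 extracts from the same model "the difference and associated 95% CI and p-value between each tildacerfont dose and placebo at each of 4, 8 and 12 weeks". Appendix D's model statement carries no df option. Appendix E's text builds its absolute-scale interval on a t quantile with the primary model's error df, without saying how that is computed. Kenward-Roger is requested only in SAP 13.5.5: "MODEL VAL = VTYPE / SOLUTION DDFM=KR".

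**Supportive MMRM.** SAP 13.3.5.1, which 13.4.1.1 re-uses, names subject as a random effect and then says: "Within-subject correlations will be modeled using an unstructured covariance structure". Toeplitz, AR(1) and compound symmetry follow as fallbacks.

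**The concern.** There are two separate issues.

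1. An ML likelihood-ratio statistic for fixed effects is chi-square only in large samples. In a trial of 72 subjects (60 if 15 per arm are evaluable) it tends to be too large. Under 13.3.3 this p-value decides whether there is evidence of a treatment effect, so its real level should match the stated one.

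2. A t-based interval or p-value needs a denominator df, and the SAP gives no rule for it in this model. The natural candidate, the residual df, depends on which random terms survive the zero-variance rule. Two analysts following the text could therefore report different intervals from the same data. SAP 10.5 also orders dose-versus-placebo tests of the primary endpoint at 0.05 and names no other model for them, so the choice may bear on those p-values too.

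**Working it through.** **Inputs.** Protocol 9.2 and SAP 7: 15 per group, 15% dropout, four arms. SAP 13.1: three post-baseline visits. SAP 13.3.2 and 13.3.3: model, ML, chi-square, 10%. Assumed, because the documents give no figure: the log-scale variance components.

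**The plan's own figures.** 15 / (1 − 0.15) = 17.6, rounded up to 18 per arm; 18 × 4 = 72. The df is 3 linear plus 3 quadratic interactions = 6. Both reproduce.

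**Size of the joint test, analytic.** With complete data, the tested terms concern p = 2 within-subject contrasts (linear and quadratic) across q = 3 treatment df. For an unstructured covariance the ML statistic is −N ln Λ (Wilks). Bartlett's approximation says that −[ν − (p − q + 1)/2] ln Λ is close to chi-square on pq = 6 df, with ν = N − 4. Here (2 − 3 + 1)/2 = 0, so the ML statistic behaves as N/(N − 4) times a chi-square on 6 df.

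| | N = 72 | N = 60 |
|---|---|---|
| 10% critical value 10.645 × (N − 4)/N | 10.053 | 9.935 |
| True size at nominal 10% | 12.2% | 12.7% |
| 5% critical value 12.592 × (N − 4)/N | 11.892 | 11.752 |
| True size at nominal 5% | 6.4% | 6.8% |

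**Size of the joint test, simulated.** Null data were fitted with the SAP 13.3.2 model: independent random effects, variances bounded at zero, ML, visits at days 28/56/84 ± 3, three covariates, complete data. There were 3,000 replicates per setting (1,800 for the last), with Monte Carlo SE 0.6–0.8 points. Rejection at nominal 10%:

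| Assumed covariance | 18 per arm | 15 per arm |
|---|---|---|
| Compound symmetry, 0.6 | 11.9% | 11.6% |
| AR(1), 0.7 | 11.4% | 12.2% |
| Random coefficients, setting 1 | 11.7% | 12.7% |
| Random coefficients, setting 2 | 12.7% | 12.7% |
| Random coefficients, setting 3 | 12.9% | 12.4% |

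At nominal 5% the range was 5.4–7.1%. An exact Wilks F-test on the same data rejected 8.6–11.0% at nominal 10%, so a small-sample reference brings the level back to about 10%.

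**Residual df, N − rank[X Z].** 72 × 3 = 216 rows.
- All three random terms: each subject's block (1, t, t²) at three distinct times has rank 3, so Z alone has rank 216. 216 − 216 = 0.
- Random quadratic dropped: Z has rank 144 and X adds 4 (one t² column per arm). 216 − 148 = 68.
- Random intercept only: Z has rank 72 and X adds 8. 216 − 80 = 136.

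Missing visits do not help: with 15% dropout the count was 200 − 200 = 0.

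**Coverage.** Non-coverage of the 95% interval for dose versus placebo at 12 weeks was 3.9–6.9% with a normal quantile and 3.6–6.3% with t on n − 7 df.

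**MMRM parameter count.** Three visits have 6 distinct covariance elements. Unstructured residuals plus a random subject variance give 7 parameters of rank 6. Toeplitz plus subject gives 4 of rank 3, and compound symmetry plus subject 3 of rank 2. AR(1) plus subject gives 3 of rank 3. Only the last is identifiable.

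**The case against.** The case for leaving the plan alone has real content.

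- **The inflation is small.** It is about 1.5 to 3 points on a 10% test in a Phase IIb study, and interval miscoverage is modest. This stands, and it limits how serious the point is.
- **ML is the proper likelihood for comparing models with different fixed effects.** This is true. The fault is the uncorrected reference distribution, not the choice of ML for that comparison.
- **Appendix E's example code avoids the df problem.** It fits an unstructured repeated-measures model with no random statement and takes its df from there. This also stands, but the code then disagrees with the appendix text, which points to the primary model.
- **The MMRM wording is loose rather than harmful.** A random intercept added to unstructured residuals leaves the marginal covariance unstructured, so the fixed-effect model is unchanged. This is fair; it is a minor correction.

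A reader might also go further than the evidence allows:

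- *That three random coefficients on three visits cause the inflation.* They do not. The four-parameter covariance is identifiable from three visits. With compound-symmetric data, where variance components collapsed to zero in about 95% of trials, the size was still 11.6–11.9%.
- *That the contrasts will print without an interval or p-value.* That depends on software defaults. SAS was not run, and the documents do not describe its defaults. What is established is that the residual df is 0 and no method is named.
- *That independent random coefficients cannot give correlation that falls with lag.* They can. With variances 1, 0.1 and 0.02 (time in 28-day units) and residual 0.3, the correlations are 0.76 (days 28–56), 0.84 (56–84) and 0.64 (28–84). The longest lag has the lowest correlation.

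**Conclusion.** The point holds, as something that should be fixed. The nominal 10% primary test runs at about 11.5–13%, or about 5.5–7% if read at 5%. The cause is the uncorrected ML chi-square reference. The simulated figures assume complete data and assumed variance components; the analytic 12.2% and 12.7% use the unstructured-covariance analogue with complete data and agree with them.

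Separately, the dose-versus-placebo contrasts have no stated df method. The residual df is 0, or 68 once the random quadratic is dropped, so the error df in Appendix E's text is not usable as written. The practical cost in coverage is modest, at 3.6–6.9% against 5%. The main loss is that the plan does not fix a single interval for a given dataset.

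Which nominal level applies is a different question. The 10% in 13.3.3 does not match the two-sided 0.05 in Protocol 9.4.1 and SAP 9.2 and 10.5, and that needs its own reconciliation.

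**What to change.** 1. In SAP 13.3.3, test the six treatment-by-time and treatment-by-time-squared terms jointly against a small-sample reference, for example a REML fit with a Kenward-Roger F-test in place of the ML chi-square difference. The check above used an exact Wilks test, not the Kenward-Roger F, so a short null simulation before database lock would be prudent.
2. State `DDFM=KR` for every dose-versus-placebo contrast in 13.4.1 and Appendix D, and as the source of the df in Appendix E. Carry this to the 17-OHP analyses that copy the method.
3. Align Appendix E's text and code on one model.
4. In 13.3.5.1, remove subject as a random effect. It duplicates the unstructured, Toeplitz and compound-symmetry residual structures.

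An unstructured 3 × 3 within-subject covariance in place of the random coefficients is an acceptable option but is not required.

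The cost is SAP wording and a few lines of SAS, with no new data. The downside is slightly less favourable p-values.
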